10.6 Analyses

Due to US federally mandated reporting of outcomes to clinicaltrials.gov, the timing of initiating analyses for those outcomes, are likely to occur prior to study follow-up being completed. Therefore, there will be separate primary and secondary statistical analyses reports to cover all the analyses listed below.

10.6.1 Primary Efficacy Analysis

The primary efficacy outcome (SVR) will be estimated with a point-wise estimate as well as a 95%, two-sided CI. The confidence bound will be calculated with binomial distribution according to the method of Wilson (Score based interval). The impact of missingness contributing to the (lowering of the) SVR response rate will be addressed by providing the various reasons for non-SVR (e.g., discontinued treatment early due to various reasons including intolerance, HCV RNA \geq LLOQ, missing evaluation for SVR (and reasons as known), and the number of participants meeting each reason for non-SVR.

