10.2 Outcome Measures

10.2.1 Primary Outcome Measures

- 10.2.1.1 Efficacy: Sustained virologic response defined as <LLOQ of HCV RNA in plasma from the earliest sample drawn at least 22 weeks following study entry. Missing results will be treated as SVR non-responders.
- 10.2.1.2 Safety: SAEs as defined by International Council for Harmonization (ICH) guidelines occurring from study entry until 24 weeks following study entry.

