10.4 Sample Size and Accrual

The sample size for this single-arm study is 400 participants.

This sample size was chosen for benchmark properties listed below regarding the use of efficacy data from this study to informing the utility and feasibility of future studies of the MINMON approach, and the precision (based on CI width) about SVR efficacy outcome estimates.

Table [10.4-1](#) below describes SVR benchmarks and their properties.

The high benchmark is defined as when the lower confidence limit of the 2-sided 95% CI about the SVR estimate is strictly greater than 96%. Observing 392 or more SVR responders out of 400 participants (i.e., $\geq 98\%$ SVR responders) would meet this benchmark. Under a true SVR rate of 97%, there is only a small probability (0.15) of observing this benchmark with the study sample size of 400. However, as the true SVR rate becomes higher, the probability of observing this benchmark also increases (while holding the sample size at 400 participants). For instance, if the true SVR rate were 98.5%, then there is 0.85 probability of observing this high benchmark in the proposed study sample size of 400. If a high benchmark were observed, then a future RCT may not be needed, as the high benchmark implies that the SVR for the MINMON strategy exceeds 96%.

The low benchmark is defined as when the upper confidence limit of the 2-sided 95% CI about the SVR estimate is strictly less than 95%. Observing 371 or fewer SVR responders out of 400 participants (i.e., $\leq 92.8\%$ SVR responders) would meet this benchmark. Properties of possible scenarios are given in Table [10.4-1](#).

If neither the high nor low benchmark is met, a future RCT of the MINMON approach versus SOC may be desired, and efficacy estimates from this study could be used to inform the design and sample size of that study.

The low and high SVR benchmarks described above and in Table 10.4-1 below were chosen to represent what is currently thought to be reasonable SVR rates based on studies presented and published, including clinical trials, as well as studies reporting use of this DAA regimen outside the context of a clinical trial.

Properties of this study's sample size regarding probability of not observing either benchmark

Table [10.4-2](#) below summarizes the various probabilities that neither of the benchmarks (HIGH or LOW, as described above), are observed under a range of various true rates of SVR.

Table 10.4-1. SVR benchmarks and their properties

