The sample size calculation has not been adjusted for losses to study follow-up as the definition of the primary efficacy outcome includes imputing missing evaluations as SVR non-responders. The impact of missingness contributing to the (lowering of the) SVR response rate will be addressed by both enumerating what led to non-SVR responder classification such as the following: missing HCV RNA values for SVR evaluation, HCV

RNA values observed >the assay LLOQ, early stopping of study treatment (e.g., for intolerance, etc.).

Assuming uniform accrual of 25 participants per month, total accrual to the study would be completed in 16 months. If initial accrual is assumed to be slower, at rates of 10 participants per month for the first 6 months, 15 participants per month for the next 6 months, and 20 participants per month for the remaining time, the total accrual time would be about 24 months.

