outcomes. At interim reviews, SVR will be calculated only among those with potential to contribute to SVR (by having at least 22 weeks elapsed since study entry). Imputation of missing SVR evaluation as non-SVR response will only occur for participants for whom more than 76 weeks since study enrollment has elapsed. In other words, early study discontinuations prior to week 22 will not be counted in SVR estimation at interim review, as these could bias the estimation of SVR towards futility. Instead, these early study discontinuations prior to week 22 (before available for SVR evaluation), and others missing SVR evaluation, will contribute to the interim monitoring trigger below.

If the analysis sample for the initial planned review for efficacy as outlined above includes fewer than 40% participants from non-US clinical research sites, then a second planned review of efficacy will be triggered when SVR outcomes are available on approximately 230 participants (with the upper limit of US participants of 132, this estimates at least 40% non-US representation in the second efficacy look interim analysis sample). The same analysis plan and monitoring bounds as defined in the first look above would be applied to this second look at SVR.

An unplanned interim review will be triggered if, at any time, more than 20 persons are not evaluable for the SVR outcome before study discontinuation or 76 weeks following study enrollment. Another trigger for an unplanned interim review is if, at any time, the number of participants experiencing an SAE exceeds 5% of the interim analysis dataset, and the absolute number of participants with SAEs at least 10 (as 5% was the observed upper bound of the 95% CI on number of participants with any SAE from the ASTRAL-5 trial).

Any/all SMC reviews will include administrative/trial conduct data as well as safety data according to the safety-related outcomes enumerated above.

The following routine monitoring reports are distributed to core team and are detailed in the study monitoring plan (SMP): screening, accrual, data delinquency, study status, data and sample completeness, with attention to evaluation and timing of SVR outcome. The routine safety monitoring report is distributed to the DAIDS Clinical Representative and a subset of the core team (to include the study chairs) every 3 months.

Further details about monitoring of this study are available in the SMP.

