4.1 Primary Outcome Measures

4.1.1 Primary Efficacy Outcome Measure

Measure Title: *Percentage of Participants with Sustained Virologic Response 12 (SVR12)*

Measure Description: *SVR12 was defined as plasma HCV RNA less than the lower limit of quantification (LLOQ) from the earliest sample drawn at least 22 weeks following study treatment initiation (i.e. at a visit scheduled at least 10 weeks after scheduled end of study treatment). Participants without any HCV RNA result at least 22 weeks after treatment initiation will be considered as having HCV RNA greater than the LLOQ.*

A two-sided 95%, confidence interval was calculated for this percentage using the Wilson (score) method.

Time Frame: *At least 22 weeks and up to 76 weeks from treatment initiation.*

Population Description: *Participants who enrolled and received first dose of study medication.*

Associated study objective: *“To estimate SVR (defined as HCV RNA < lower limit of quantification [LLOQ] at least 10 weeks after the end of treatment [EOT] [which is at least 22 weeks from the study entry visit date]).”*

Details: Due to the definition of SVR outcome measure, missing HCV RNA results will lower the overall percentage of participants with SVR. Therefore, various reasons for non-SVR (e.g., discontinued treatment early due to various reasons including intolerance, observed HCV RNA \geq LLOQ, missing evaluation for SVR (and reasons as known), and the number of participants meeting each reason for non-SVR, will be presented in order to interpret the overall SVR sample estimate.

For interim analyses: Interim analysis is planned when SVR outcomes are available for approximately 100 participants. At interim reviews, SVR will be calculated only among those with potential to contribute to SVR (by having at least 22 weeks elapsed since study entry). Imputation of missing SVR evaluation as non-SVR response will only occur for participants for whom more than 76 weeks since study enrollment has elapsed. In other words, early study discontinuations prior to week 22 will not be counted in SVR estimation at interim review, as these could bias the estimation of SVR towards futility. Instead, these early study discontinuations prior to week 22 (before available for SVR evaluation), and others missing SVR evaluation, will contribute to the interim monitoring

trigger. For more details, refer to Overview of Formal Interim Monitoring of section 3.5 above.

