5.1.4 Analysis Approaches

The analysis of each objective addressed in this SAP will be conducted using the appropriate analysis sample as defined in section 4.1.

As this is a single arm study, the primary descriptive and statistical inference on outcomes will be performed on the entire specified analysis sample as a single group, and focus on estimation. However, as there exist key subgroups upon which separate estimates for outcomes is desired, analyses will often (as specified below) be repeated within subgroups defined by the following:

- **Country** (to help inform each MOH or other, policy groups, as well as serving as an imperfect surrogate for HCV genotype)
- **Cirrhosis status** (compensated cirrhotic and non-cirrhotic by classification by FIB-4 score)
- **HIV-1 infection status** (positive and negative)
- **Sex assigned at birth** (female and male)
- **If data are available, by HCV genotype**

However, there are no plans to perform formal hypothesis testing for differences in outcomes among subgroups.

All statistical hypothesis testing at final analysis, will use the nominal significance level of 0.05. See detailed specifications at interim reviews for alternative significance levels.

6 Report Contents

Detailed descriptions of the content of each of the following sections are given in the AIP:

1. CONSORT Diagram (final analysis only)
2. Accrual
3. Baseline characteristics
4. Study conduct
 - a. Study status and follow-up
 - b. Study medication disposition
 - c. Remote contact at week 4
 - d. Adherence of medication, premature discontinuation of study treatment
 - e. Remote contact at week 22
 - f. Data and specimen availability (other than for SVR evaluation)
 - g. Unplanned Clinic Visits (number/reasons)
5. Safety
 - a. Primary Safety Outcome Measure: SAEs within 24 weeks
 - b. Secondary Safety Outcome Measure: other AEs within 24 weeks
 - c. Summary of other AEs (all AEs after 24 weeks)
 - d. Summary of pregnancies that occur during study participation
 - e. Summary of HIV-1 RNA among PLWH at Week 24/SVR visit
6. Efficacy
 - a. Study visit of SVR collection
 - b. SVR12 estimation
 - i. Summary of details (e.g assay, LLOQ, lab) used to evaluate SVR
 - ii. Estimation within subgroups
 - iii. Reasons for non-SVR
 - iv. Summary of participants not achieving SVR (baseline characteristics, study/treatment disposition, safety and tolerability information)
 - c. Summary of HCV RASs among participant not achieving SVR [if data available]

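### Does the final analysis need a pre-specified SVR estimate among tested participants beside the missing-equals-failure result?

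*Protocol*

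**What the plan says.** Both documents apply the same rule. Protocol 10.2.1 states: "Missing results will be treated as SVR non-responders". SAP 4.1.1 states: "Participants without any HCV RNA result at least 22 weeks after treatment initiation will be considered as having HCV RNA greater than the LLOQ". At final analysis the efficacy sample is everyone who started study medication (SAP 5.1.3), and the interval is a two-sided 95% Wilson interval (protocol 10.6.1, SAP 4.1.1).

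Protocol 10.4 defines two benchmarks on this estimate. High requires a lower limit above 96%, which means at least 392 of 400. Low requires an upper limit below 95%, which means at most 371 of 400. Between them, "If neither the high nor low benchmark is met, a future RCT of the MINMON approach versus SOC may be desired".

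The plan deals with missing results by reporting reasons. Protocol 10.6.1 says "The impact of missingness contributing to the (lowering of the) SVR response rate will be addressed by providing the various reasons for non-SVR", with the number of participants under each reason. Its examples list HCV RNA at or above the LLOQ separately from a missing evaluation. SAP 4.1.1 repeats this and gives its purpose: "in order to interpret the overall SVR sample estimate". SAP section 6 adds tabulations of the visit at which SVR was collected and of the reasons for non-SVR, and a "Summary of participants not achieving SVR (baseline characteristics, study/treatment disposition, safety and tolerability information").

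During the trial, "An unplanned interim review will be triggered if, at any time, more than 20 persons are not evaluable for the SVR outcome" (protocol 10.5.1).

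**The concern.** A missed visit and a virologic failure count the same in the primary estimate but mean different things. The protocol rationale (2.2) accepts that a cured person who does not return is scored as a failure. A low-benchmark result could therefore reflect people who were not retested rather than people who were not cured. The benchmarks are meant to inform whether a randomised trial is wanted and whether the approach should be reconsidered.

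Three features make the omission more noticeable:

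- Interim SVR rests mainly on observed results. The protocol (10.5.1) and SAP (4.1.1) give the reason: counting early discontinuations as failures could bias the estimate towards futility.
- The cost analysis has a sensitivity analysis for loss to follow-up (protocol 12.3 and 12.5), but its output is cost per SVR, not an SVR estimate.
- Protocol 10.4 says the effect of missing results "will be addressed by both enumerating what led to non-SVR responder classification", and the second element that the word both promises never appears.

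A reader could fairly ask why the final efficacy analysis has no estimate among tested participants fixed in advance.

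**Working it through.** **Inputs from the documents.** N = 400; two-sided 95% Wilson interval; high benchmark if the lower limit exceeds 96%, low benchmark if the upper limit is below 95%; missing = non-response; review trigger at more than 20 non-evaluable (protocol 10.2.1, 10.4, 10.5.1, 10.6.1).

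**Assumed inputs.** The documents give no expected missingness for this trial, so 1 to 7% is used, missing at random. Cure among those tested is taken as 96 to 98.5%, within the range of hypothesised rates in protocol 10.4.

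**Formula.** With p = x/n and z = 1.96, the Wilson limits are [p + z²/(2n) ± z·√(p(1−p)/n + z²/(4n²))] / (1 + z²/n).

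**1. The plan's cut-offs reproduce.** For 392/400 the centre is (0.98 + 0.00480)/1.00960 = 0.9754 and the half-width is 1.96 × √(0.0000490 + 0.0000060)/1.00960 = 0.0144, so the lower limit is 96.10%.

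| Responders of 400 | Relevant limit | Reading |
|---|---|---|
| 392 | lower 96.10% | high |
| 391 | lower 95.78% | neither |
| 372 | upper 95.11% | neither |
| 371 | upper 94.90% | low |

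The binomial probability of the high benchmark at 98.5% is 0.849, against 0.85 in Table 10.4-1.

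**2. Missed visits alone.** 400 − 9 = 391, so 9 missing (9/400 = 2.25%) rule out high. 400 − 29 = 371, so 29 missing (29/400 = 7.25%) force low.

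**3. The two estimates side by side** (M missing, f observed failures; primary (400−M−f)/400, tested-only (400−M−f)/(400−M)).

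| M | f | Primary | Tested-only |
|---|---|---|---|
| 12 | 6 | 382/400 = 95.5% (93.0–97.1), neither | 382/388 = 98.5% (96.7–99.3), high |
| 20 | 9 | 371/400 = 92.75% (89.8–94.9), low | 371/380 = 97.6% (95.6–98.7), neither |
| 22 | 7 | 371/400 = 92.75% (89.8–94.9), low | 371/378 = 98.1% (96.2–99.1), high |

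The last row has the smallest M at which the readings are fully opposed. It lies just above the trigger of more than 20 non-evaluable.

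**4. How often the readings differ.** Take M ~ Binomial(400, m) and f ~ Binomial(400 − M, 1 − cure). At m = 3%:

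| Cure among tested | P(primary neither, tested-only high) | P(primary low, tested-only neither) |
|---|---|---|
| 96% | 0.02 | 0.41 |
| 97% | 0.13 | 0.15 |
| 98% | 0.53 | 0.03 |
| 98.5% | 0.80 | 0.01 |

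Full opposition (low against high) has probability about 0.001 or less at 3% missing in every row. At 98.5% cure it rises to 0.16 at 5% missing and 0.63 at 7%. The chance of more than 20 missing is then 0.44 and 0.93, so the review trigger would often have been met.

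**5. What the added estimate would change.** The primary proportion, its interval and the benchmark reading are all computed on the full analysis sample and stay as they are. The tested-only figure uses x, the number of missing results, and the Wilson formula. The first two come out of planned tabulations and the third is already specified.

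**The case for a change.** The strongest argument for a change is that pre-specification costs one sentence, while a ratio worked out after the result is known leaves its denominator and status open. The readings differ often under plausible conditions, and the review trigger adds nothing to the final report. There is also a practical difficulty. The list of reasons for non-SVR puts early treatment discontinuation beside missing evaluation. If each person were assigned a single reason, that table alone might not give the number tested.

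Part of this stands. The estimate is useful, a careful report would show it, and the supplied text does not name it. The scope for later choice is small, however. The sample rule (earliest result from 22 weeks), the LLOQ criterion and the interval method are fixed, and the tabulation of SVR collection visits in SAP section 6 should identify who was tested. The SAP also defers the detailed content of each report section to the Analysis Implementation Plan, which is not among the documents and may already include this table.

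The tested-only figure has its own weakness: it is optimistic if non-returners are cured less often. Its overstatement is m × (0.985 − c), where c is cure among non-returners. With c assumed as low as 0.70, that is 0.03 × 0.285 = 0.9 points at 3% missing and 0.05 × 0.285 = 1.4 points at 5%. It could not replace the primary reading.

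**Conclusion.** No change to the plan is needed. Scoring a missed evaluation as failure is stated openly, errs on the conservative side, and fits the question: the rationale treats confirmation of SVR as one of two critical components, so failure to return is partly a failure of the strategy. The plan says that missing results lower SVR and commits to the counts a reader needs to see by how much. The unfinished phrase in protocol 10.4 is a drafting slip, and 10.6.1 is the operative text.

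The sensitivity to missed visits is real: 9 missing results rule out the high benchmark and 29 force the low one. How often the two estimates would read differently depends heavily on assumed cure. At 3% missing at random, the probability of neither against high runs from 0.02 at 96% cure to 0.80 at 98.5%, so no single figure describes it. The benchmark consequences in protocol 10.4 are also worded as possibilities rather than decision rules.

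Showing a tested-only proportion with its Wilson interval and the number not tested, with benchmarks read on the primary estimate only, would be a reasonable choice for the report. It is a presentation option. The conclusion assumes that the planned counts are reported so that missing results can be told apart from HCV RNA at or above the LLOQ, as both documents say.

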10.6.2 Primary Safety Analysis

The primary safety outcome of SAEs will be enumerated, summarized and described for all qualifying outcomes. The number and relative frequency of participants experiencing one or more SAEs will also be summarized, and a CI about the probability of experiencing a SAE will be calculated (using CI methods as described above).

10.6.3 Secondary Outcomes Analysis

Premature discontinuation of study treatment will be defined from participant self-report either via remote contact prior to SVR evaluation, or at an unplanned visit or by retrospective recall at the week 24 or SVR evaluation visit (whichever occurs first). Those participants missing information from all these mechanisms will be assumed to have prematurely discontinued. The proportion of premature study treatment discontinuation will be estimated and a CI calculated to summarize the range of plausible values using methods parallel to other dichotomous outcomes described above.

Non-serious AEs will be summarized by the Medical Dictionary of Regulatory Affairs (MeDDRA) System Organ Class by the reporting types described in section 7.2.

Those who do not achieve SVR with an observed HCV RNA \geq LLOQ will have both baseline and SVR specimens tested for HCV RASs. Participants in this subset with HCV RASs present in their SVR specimen that were not present in their baseline specimen will be enumerated along with the relative frequencies of new RASs. A description of the observed RASs will also be provided.

Among SVR responders, HCV RNA post SVR follow-up (i.e., Step 2) will be used to evaluate for the HCV reinfection outcome. Detectable HCV RNA, with and HCV sequence distinct from the baseline sequence will qualify for the outcome of HCV reinfection. The absolute number (and relative frequency) of participants meeting this outcome will be summarized along with a 95% CI using methods as described for other dichotomous study outcomes.

Among SVR responders, HCV disease regression will be defined by the absolute change between baseline FIB-4 value and the final study FIB-4 value. The distribution of these absolute changes will also be described using key percentiles.

Further details are outlined in the study's Statistical Analysis Plan (SAP).

